For study patients in whom Mavyret™ therapy is being considered, exclusion criteria includes patients on the following medications who cannot stop therapy: carbamazepine, rifampin, St. John's wort, and ethinyl estradiol-containing oral contraceptives.

For any patient receiving pan-genotypic DAA therapy, the corresponding drug administration instructions will be followed as listed in the Mavyret™ package insert. This includes review of potentially significant drug interactions and discontinuation or alteration in dosages and monitoring as recommended. The Tables that will be followed can be found on the Mavyret™ package insert pg. 8 Table 5.

A subset of patients awaiting liver transplant also require kidney transplant. The efficacy of DAAs in the treatment of donor derived HCV infection in kidney transplant has been documented in recent trials at the University of Pennsylvania and John's Hopkins Hospitals. Given this recent data, patients requiring simultaneous liver-kidney transplant (SLKT) are being considered for enrollment in this study. If patients screened for enrollment meet inclusion criteria for liver transplant, they will not be excluded based on the need for SLKT. Their case will be discussed with the study's transplant nephrologist, and enrolled accordingly with plans to update UNET listing status for SLKT transplant. As far as DAA therapy is concerned, if a patient is already undergoing treatment based on receipt of an HCV-positive liver, there are no changes in Mavyret™ therapy duration that would be required if a kidney transplant is also performed. In patients receiving SLKT, a patient's renal function and potential for delayed graft function (DGF) will come into play when initiating DAA treatment..

Standard of care at Partners includes confirming that female patients are not pregnant at the time of organ transplantation. For women of childbearing potential, a urine pregnancy test will be performed as needed per standard of care prior to enrollment. A negative result will be required at the time of transplant and prior to continuing study treatment.

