The **screening visit** will take place within an estimated 1-week to 6 months prior to liver transplantation. For all patients enrolled in the protocol, their transplant case will be reviewed on a weekly, bi-weekly, or monthly basis based on MELD and position on the waitlist as per usual active transplant waitlist patient management.

Day 0 represents the day of liver transplantation; study DAA treatment will be initiated within 7 days of liver transplant. After initiation of therapy, each subject will receive their study drug daily through 12-week course completion.

Patients will initially provide in person or remote written informed consent to be “waitlisted” for HCV-positive donor livers under this protocol. At the time a liver transplant becomes available, the “waitlisted” patients will be contacted and again sign informed consent for transplantation (standard of care surgical consent).

Upon receiving notification that an HCV-antibody (Ab) positive donor organ is available, we will review if the organ is nucleic acid testing (NAT) positive or negative. A pre-emptive treatment approach will be used in patients receiving NAT-positive donor organs, and a reactive treatment approach will be performed in patients receiving NAT-negative donor organs, as outlined below:

A study patient who receives an HCV NAT-negative donor liver (or liver and kidney) will be followed with HCV viral load (VL) testing per study protocol on study days 0, 1, 3, 7, 14, 28, 42, 56, 84, 112, 168, 252, and 365. Additional monitoring will be obtained if needed based on new LFT abnormalities.

- If the study patient does not develop a positive VL during this 365 day duration they will not undergo treatment with DAA therapy.
- If the study patient does demonstrate seroconversion with a newly positive HCV VL then we will initiate pan-genotypic therapy per study protocol.

Upon receiving notification that an HCV-positive donor organ is available with plans for transplantation, a patient’s case will be reviewed and the appropriate DAA selected based on individual patient factors the study subject will be scheduled to receive treatment with the below pan-genotypic DAA:

- co-formulated glecaprevir (300mg)/pibrentasvir (120mg) (Mavyret™) given orally for a duration of 12 weeks post-transplantation.

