Achievement of Sustained Virologic Response (SVR). Patients who received an HCV-positive donor liver who have an undetectable viral load 12 weeks after completing therapy (SVR 12) are liver recipient patients in whom the use of DAA treatment has successfully prevented the development of chronic HCV infection. If during monitoring while on DAA therapy a positive viral load is detected, a plan may be made to extend the patient's course of Mavyret™ beyond 12 weeks. We may also add additional Hep C medications to increase the chance of curing HCV infection. If this happens, we will plan to review all of these details in person with the patient and determine, based on recent updates and clinical practice, the best regimen with which to treat the patient and achieve HCV cure.

The detailed protocol version of this study dated 3/13/2017 was reviewed by the food and drug administration (FDA). It was found that preemptive treatment with DAA therapy for donor HCV positive to recipient HCV negative liver transplant was determined to be IND exempt; this exemption letter has been uploaded to insight.

VI. Biostatistical Analysis

Variables/Time Points of Interest

The primary variable of interest will be HCV RNA at the multiple time-points assessed during and after treatment.

The primary efficacy outcome “prevention of HCV infection in liver recipient” will be determined by a negative HCV RNA test at 12 weeks following therapy completion (SVR 12).

The safety outcomes include summation of treatment related adverse events and transplant rejection or patient mortality. On treatment eGFR, proteinuria, hemoglobin, and liver function tests will be summarized to assess safety.

Statistical Methods

Patient characteristics for this cohort (N=50) will be presented with summary statistics for baseline demographics and clinical variables. The SVR12 rate will be presented and 95% CI constructed with the exact test. Mean and standard deviation for on-treatment laboratory values will be presented to analyze safety.

Power/Sample Size:

This is a pilot study. Up to 300 patients will be enrolled (consented for the possible receipt of an HCV-positive organ), the total number of patients eligible to receive transplant and study drug = 50.

VII. Risks and Discomforts

Psychological risk

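### The renal safety summary does not separate simultaneous liver-kidney recipients, so mean on-treatment eGFR and proteinuria would mix two different renal populations

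*Combined protocol and SAP*

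**What the plan says.** The study title covers both liver and simultaneous liver-kidney transplant. Section III (Subject Selection) says of candidates who meet the liver criteria that "they will not be excluded based on the need for SLKT". It sets no cap or target number for them. The same section says that in SLKT recipients "renal function and potential for delayed graft function (DGF) will come into play when initiating DAA treatment".

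Section V (Study Procedures) states that "study DAA treatment will be initiated within 7 days of liver transplant". Recipients of NAT-negative livers who never develop a positive viral load are not treated.

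Section VI (Biostatistical Analysis) says under Variables/Time Points of Interest: "On treatment eGFR, proteinuria, hemoglobin, and liver function tests will be summarized to assess safety". Under Statistical Methods the stated method is: "Mean and standard deviation for on-treatment laboratory values will be presented to analyze safety". The figure of 50 appears in the sentence on baseline description, "Patient characteristics for this cohort (N=50) will be presented with summary statistics for baseline demographics and clinical variables", and under sample size, "the total number of patients eligible to receive transplant and study drug = 50". The laboratory sentence has no denominator of its own. The documents do not mention a split by transplant type, a change from baseline, or a count of patients with renal decline.

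**The concern.** Safety and tolerability is Aim 2, and eGFR and proteinuria are the renal measures named for it. A liver-only recipient's on-treatment eGFR describes native kidneys after liver transplantation. An SLKT recipient's describes mainly a newly placed graft, which may recover quickly or be slow to function. DAA treatment starts within 7 days of surgery, so early graft function can fall inside the on-treatment window.

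A mean over both groups describes neither. Its level and spread depend on how many SLKT recipients happen to enrol and how their grafts behave, and neither has to do with the drug. The study has one arm and no independent DSMB, so this descriptive table is the only stated renal analysis. A reader could be falsely reassured by it or falsely alarmed.

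**Working it through.** **Is there a planned figure to reproduce?** No. The plan states no expected eGFR, SD, SLKT count or renal threshold, and 50 is given as a pilot number without derivation. The check is therefore mixture arithmetic under stated assumptions.

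**Inputs.** From the documents: up to 50 transplanted and eligible for study drug; SLKT eligible without a cap. Assumed, because the documents give no values: *k* SLKT recipients among *n* = 50 treated; liver-only eGFR change -*D*; SLKT eGFR change +*R*; within-group SD *s* = 15 (all in mL/min/1.73 m²).

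**Effect on the planned statistic (a mean of levels).** Let Δ be the SLKT mean minus the liver-only mean and *p* = *k*/*n*.
- Combined mean = liver-only mean + *p*Δ.
- Combined SD = √(*s*² + *p*(1 - *p*)Δ²).

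The mean moves up if the grafts work better than the native kidneys (Δ > 0). It moves down if delayed graft function keeps them worse (Δ < 0). The SD rises either way. With 5 SLKT recipients of 50 the shift is one tenth of Δ, and with 10 it is one fifth.

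**Illustration on the change scale.** The plan does not compute a change. The scale is used here only because it shows dilution and masking directly.

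Combined change = [*kR* - (50 - *k*)*D*]/50.

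| SLKT of 50 | *D* = 10, *R* = 40 | *D* = 10, *R* = 20 |
|---|---|---|
| 2 | (80 - 480)/50 = -8 | (40 - 480)/50 = -8.8 |
| 5 | (200 - 450)/50 = -5 | (100 - 450)/50 = -7 |
| 10 | (400 - 400)/50 = 0 | (200 - 400)/50 = -4 |

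The liver-only change is -10 in every cell.

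**When would a fall vanish completely?** When *k*/50 = *D*/(*D* + *R*), that is *k* = 50*D*/(*D* + *R*):
- *D* = 10: *k* = 16.7 (*R* = 20), 10 (*R* = 40), 8.3 (*R* = 50).
- *D* = 5: *k* = 10 (*R* = 20), 5.6 (*R* = 40), 4.5 (*R* = 50).

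**Spread and precision** (*D* = 10, *R* = 40, so the group means differ by 50; *s* = 15; 95% CI = mean ± 1.96 SD/√*n*):
- *k* = 5: SD = √(225 + 0.1 × 0.9 × 2500) = √450 = 21.2. Combined change -5.0 (-10.9 to 0.9). Liver-only, *n* = 45: -10 (-14.4 to -5.6).
- *k* = 10: SD = √(225 + 0.2 × 0.8 × 2500) = √625 = 25. Combined change 0.0 (-6.9 to 6.9). Liver-only, *n* = 40: -10 (-14.6 to -5.4).

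**Denominator.** Untreated NAT-negative recipients have no on-treatment values, so *n* may be below 50. Each treated SLKT recipient then weighs *k*/*n*, which exceeds *k*/50.

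**The case against.** The strongest case against has five parts.

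1. **The plan does not say the values will be combined.** True: it is silent on stratification. But an unstratified mean for a study described as one cohort is what results from following the text as written.

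2. **A reader might infer that rising SLKT eGFR will hide a liver-only decline.** The documents do not support that as a prediction. They give no eGFR course for either group. Delayed graft function could pull the mean down instead, and part of any graft recovery may come before the first dose. The planned statistic is a mean of levels, so cancellation of a fall by a rise is an illustration, not an output of the plan. Nor does Section III's remark that "potential for delayed graft function (DGF) will come into play when initiating DAA treatment" say that eGFR will follow a different course; it concerns the start of treatment.

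3. **The SLKT number may be very small.** This stands. With 2 SLKT recipients the illustration shows dilution only (-8 or -8.8 against -10).

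4. **Other safeguards exist.** On-treatment laboratory review (Section V), adverse event assessment at each treatment visit, quarterly safety meetings (Section IX) and discussion of SLKT cases with the study's transplant nephrologist (Section III) may well catch an individual decline. They do not supply an interpretable summary for the report.

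5. **A split would not show causation.** This also stands. With one arm, recent major surgery and immunosuppression, a liver-only decline could not be attributed to the DAA.

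**Conclusion.** The point holds as a reporting weakness. As written, the plan gives only an unstratified mean and SD of on-treatment eGFR and proteinuria in a population that may include any number of SLKT recipients. That figure mixes native-kidney and new-graft function and has an inflated SD. It can dilute, mask or mimic a liver-only decline.

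The effect ranges from slight (about 1 to 2 units of a 10-unit fall with 2 SLKT recipients of 50) to complete masking (10 of 50 with an SLKT change of +40). These sizes rest on assumed changes, an assumed SLKT count and 50 treated patients. The sign also depends on the graft course. Importance is minor to moderate: the study is a descriptive pilot, no test or stopping rule is tied to eGFR, and SVR12 is unaffected.

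**What to change.** In Section VI, Statistical Methods:
- Make change from pre-dose eGFR, by visit, in DAA-treated liver-only recipients the main renal safety summary, and state the number treated. Define the pre-dose value.
- Do the same for proteinuria where a pre-dose value exists.
- Report SLKT recipients separately, as individual values if they are few.
- Leave the other laboratory values combined.

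Section V already refers to a baseline metabolic panel, so eGFR should need no new test. The text available does not show whether proteinuria is measured before dosing, hence the condition. The cost is one table split and a slightly smaller group for the main renal summary (45 instead of 50 if 5 of 50 treated patients are SLKT). The report should say that the split makes the renal summary interpretable but does not attribute a decline to the DAA.

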Direct acting antiviral agents (DAAs) have dramatically improved treatment options and outcomes for patients with HCV in both the pre- and post-transplant setting. SOLAR-1 was a large, multicenter, randomized controlled trial of sofosbuvir/ledipasvir (SOF/LED) with weight-based ribavirin in 223 liver-transplant recipients infected with HCV genotypes 1 and 4, with a wide range of liver disease severity. The cure rate for 12 weeks of combination therapy was 96%. In patients with HCV without cirrhosis in the allograft, cure rates of many DAA regimens have been reported in the range of 95% or higher. The discontinuation rate for these medications is low and side effects rare. Importantly, the sofosbuvir-based regimens do not have major interactions with the commonly used post-transplant immunosuppressive regimens.

The daily, fixed-dose, of co-formulated sofosbuvir/velapatasvir (SOF/VEL) is similarly effective to its predecessor SOF/LED but has pan-genotypic activity. It is currently recommended as a first-line therapy for treatment-naïve, noncirrhotic HCV infection for genotypes 1-5. Reported cure rates in the non-transplant setting have been high in the 98-100% range. In the ASTRAL-1, ASTRAL-2 and ASTRAL-3

studies, more than 1,000 patients have been treated with SOF/VEL with an overall cure rate of 98%, without safety or tolerability concerns in the post-transplant setting.

In light of these recent advances in HCV therapy, we believe that DAAs have the potential to play an important role in curtailing the current discard rates for HCV-positive donor livers. In this study we plan to administer DAA therapy in donor HCV-positive to recipient HCV-negative liver transplantation. We plan for use of SOF/VEL in this study. The advantage of SOF/VEL as compared to other DAAs is that it has pan-genotypic activity. This avoids the need for rush donor genotyping, and prevents losing potential good-quality organs that are infected by a genotype not covered by the other antiviral drugs that lack pan-genotypic activity.

In the fall of 2017 an additional pan-genotypic regimen, glecaprevir/pibrentasvir (GLE/PIB), trade name Mavyret, was FDA approved. The Magellan-2 study demonstrated the safety and efficacy of GLE/PIB in liver transplant adults with chronic HCV infection. We updated our initial protocol to allow for inclusion of this additional pan-genotypic agent. SOF/VEL and GLE/PIB are both pan-genotypic regimens planned for use in this study.

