Participation in research may result in undesired changes in thought process or emotion (episodes of depression, stress, guilt). Patients may experience discomfort when being asked questions about their medical history that they deem to be private.

Risks related to transplantation with an HCV-positive liver

Liver problems

While unlikely, it is possible that DAAs will not result in the same efficacy following liver transplant. If HCV is transmitted and not eradicated it is possible that HCV infection post-transplant could cause health problems, including liver injury. In the short term, infection with HCV can cause a flu-like illness that includes fatigue, nausea, fever, abdominal pain, vomiting, joint pain, and yellowing of the skin (jaundice). Although it is very rare, infection with HCV can cause severe inflammation of the liver or even liver failure, including a condition called fibrosing cholestatic hepatitis. The risk of this complication in patients without HCV who receive a transplant from a donor with HCV is unknown. This complication can be treated and cured in the majority of cases with the HCV medications.

Cirrhosis of the liver can cause someone to experience leg swelling, yellow skin, skin itching, abdominal bleeding, shortness of breath, and the abdomen to fill with fluid (ascites). Liver failure can also cause death. Based on the limited data available, it would be extremely rare for someone in the study to experience liver failure in the first few months after transplantation because the study will be giving HCV treatment right away.

In the unlikely event that the patient develops HCV infection despite DAA therapy, we will be prepared to offer 2nd line treatment and continue to reassess potential treatment options in the rapidly evolving field of HCV therapy. In the unlikely event that treatment fails, there may be continued inflammation and scarring of the liver that over many years lead to cirrhosis. If HCV causes cirrhosis, the patient is at increased risk of developing liver cancer, liver failure requiring a subsequent liver transplant, or death. Of note, we anticipate that with study drug treatment, or if necessary additional HCV therapies, we will be able to successfully eradicate HCV in our study population.

Additional risks of HCV:

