HCV can cause other types of inflammation in the body, such as arthritis, rash, anemia, nerve pain and inflammation damage to your kidney. These problems are rare, and affect less than 2% of people who have HCV. These problems should respond to effective HCV treatment.

Risks Related to Study Medications

Risks of glecaprevir/pibrentasvir (MavyretTM)

Glecaprevir/pibrentasvir (MavyretTM) is an FDA approved pan-genotypic regimen for treating HCV infection. Thousands of patients have received this medication for HCV treatment.

The adverse reactions data for MavyretTM in subjects without cirrhosis were derived from nine Phase 2 and 3 trials which evaluated approximately 2,300 subjects infected with HCV genotype 1, 2, 3, 4, 5, or 6 who received MavyretTM for 8, 12 or 16 weeks. In patients receiving MavyretTM the most common side effects were headache (13%), fatigue (11%), and nausea (8%). The overall proportion of

subjects who permanently discontinued treatment due to adverse reactions was 0.1% for subjects who received Mavyret™ for 8, 12 or 16 weeks.

The safety and tolerability of Mavyret™ after liver transplantation has not yet been extensively studied. It is possible that taking immunosuppressant medications needed after liver transplant may change the effectiveness or side effects of Mavyret™.

Risk of allergic reaction

As with any drug, an allergic reaction can occur. Allergic reactions can be mild or serious, and can even result in death in some cases. Common symptoms of an allergic reaction are rash, itching, skin problems, swelling of the face and throat, or trouble breathing. If a patient develops an allergic response to study drug the medication will be discontinued and an alternative treatment initiated

Risks Related to Study Procedures

Risks of Blood Draws

The patient may have a bruise (a black-and-blue mark) or pain where researchers take the blood samples. There is also a small risk of feeling lightheaded, fainting, or infection.

Risks to an Embryo or Fetus, or to a Breastfeeding Infant

Because the effect, if any, of Mavyret on an embryo or fetus is not known, the patient may not participate in this study if they are pregnant, breastfeeding, or planning to become pregnant. This is not a new requirement necessitated by this protocol, as patients on the liver transplant list must also agree to not become pregnant while awaiting and for a period of time post-transplantation.

VIII. Potential Benefits

Receipt of an organ

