Participants may receive a high quality liver transplant because they are enrolled in this study. For some patients, they may have not received an organ at all if the severity of their disease would have otherwise led to death while awaiting organ transplant.

Shortened wait time

Participants may spend a significantly shorter duration on the transplant waitlist than they otherwise would have if they had not been a part of the research study.

Improved patient quality of life

A liver that would have otherwise gone to waste can potentially be used to prolong the life and significantly improve morbidity for an individual.

Cost Reduction

This procedure could also eliminate costs associated with the management of end stage liver disease and hospitalization.

Increase organ donor pool

This study could increase the number of viable livers for transplant and reduce the HCV-positive liver discard rate.

IX. Monitoring and Quality Assurance

An independent data safety monitoring board (DSMB) will not be used in this study as it is an open label study, will have low enrollment, and will only take place at 1 site.

Once a patient is enrolled (transplanted with an HCV Ab+ organ), [name], [name], and [name] will meet in person every three months to review any safety concerns. More frequent meetings will occur if needed.

[name] and [name] will be regularly monitoring documents for accuracy and meeting with staff to review the status of the study. This protocol will be incorporated into the hepatology standard of care post-transplant protocol. A pool of hepatology and transplant attendings will be caring for the patients enrolled in this study. [name] will ultimately be responsible for protecting the rights, safety and welfare of all subjects enrolled in this study. In the case of [name] absence, monitoring responsibilities will be delegated to one of the subinvestigators listed on the IRB protocol application.

Adverse events will be thoroughly assessed at each treatment visit. Adverse events will be reported to the HRC as per current guidelines. We plan to comply with the reporting of any IND safety reports or any other federal regulations. The research team will work with the physician investigators to process the report of these events as they happen.

Adverse events and unanticipated problems involving risks to subjects or others will be reported to the PHRC in accordance with PHRC adverse event and unanticipated problems reporting guidelines.

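### No pre-specified rule obliges a pause in new viremic-graft transplants if treatment failures accumulate; Section IX relies on discretionary review alone

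*Combined protocol and SAP*

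**What the plan says.** Section IX (Monitoring and Quality Assurance) states: "An independent data safety monitoring board (DSMB) will not be used in this study as it is an open label study". Low enrollment and a single site are the other reasons given. In its place, three named reviewers "will meet in person every three months to review any safety concerns", and "More frequent meetings will occur if needed". Adverse events are assessed at each treatment visit, and "Adverse events and unanticipated problems involving risks to subjects or others will be reported to the PHRC".

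Section VI (Biostatistical Analysis) calls the trial a pilot and says "the total number of patients eligible to receive transplant and study drug = 50". The primary outcome, SVR12, is reported with an exact 95% confidence interval. Neither section, nor any other, gives an interim look, an acceptable or unacceptable failure rate, an event count, or a rule to pause accrual.

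Section VII (Risks and Discomforts) says "it is possible that DAAs will not result in the same efficacy following liver transplant" and that the safety and tolerability of the study drug "after liver transplantation has not yet been extensively studied". Section I reports that, in patients with HCV and no cirrhosis in the allograft, "cure rates of many DAA regimens have been reported in the range of 95% or higher".

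**The concern.** Recipients enter without HCV and are knowingly given an infected organ, so each treatment failure is an infection that the trial introduced. The protocol acknowledges uncertainty about efficacy and safety in this setting, yet it leaves the decision to go on transplanting to judgement formed after the results are seen. If failures accumulate, nothing in the plan says how many are too many. At a true failure rate of 20%, for example, 50 treated recipients would yield 50 × 0.20 = 10 expected failures, against 50 × 0.05 = 2.5 at a rate of 5%.

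The provisions for treatment failure do not fill this gap. Extending therapy or adding drugs (Section V) and second-line treatment (Section VII) concern the individual patient; neither links results to further accrual. The reasons given for having no board (open label, small, one site) do not explain the lack of a threshold, and they make one simple to operate.

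**Working it through.** The plan has no monitoring figure to reproduce. The check therefore asks when failures become known and what a simple rule would achieve.

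**Inputs from the protocol.** Treatment starts on day 0 to 7 and lasts 12 weeks (Section V). SVR12 is read 12 weeks after therapy ends, and at most 50 patients receive transplant and drug (Section VI). RNA visits include days 84, 112, 168 and 252 (Aim 3).

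**Assumptions.** A 5% reference failure rate, taken from the Section I cure rate of 95% or higher; 1, 2 or 3 transplants per month; 50 or 25 viremic-graft recipients. The protocol gives neither an accrual rate nor the split between viremic and non-viremic donors.

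**1. Readout lag.** Earliest: 0 + 84 + 84 = day 168. Latest, for an unextended course: 7 + 84 + 84 = day 175. Since 168 / 30.4 = 5.5 months, accrual of 1, 2 or 3 per month gives about 6, 11 or 17 transplants before the first SVR12 result.

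**2. Example boundary.** After each evaluable recipient n, pause when cumulative failures reach the smallest k (at least 2) with P(X ≥ k | n, 0.05) ≤ 0.025.

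| Evaluable so far | Pause at k failures | Tail probability at largest n |
|---|---|---|
| up to 5 | 2 | 0.0226 |
| 6 to 13 | 3 | 0.0245 |
| 14 to 22 | 4 | 0.0222 |
| 23 to 33 | 5 | 0.0230 |
| 34 to 45 | 6 | 0.0239 |
| 46 to 50 | 7 | 0.0118 |

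The 0.025 limit applies at each look. Repeated looks make the overall chance of a pause larger, so it must be computed separately.

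**3. Chance of ever pausing.** An exact recursion carries the failure-count distribution forward one patient at a time and removes the probability that reaches the boundary.

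| True failure rate | 50 viremic-graft recipients | 25 (assumption) |
|---|---|---|
| 5% | 6.7% | 4.9% |
| 10% | 39.8% | 24% |
| 15% | 76.5% | 50% |
| 20% | 94.1% | 73% |

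**4. Transplants performed, allowing for the lag.** If the boundary is crossed at readout n and L further transplants have been done by then, the total is min(n + L, 50); it is 50 if the boundary is never crossed. The means below take all 50 as viremic-graft recipients.

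| True failure rate | L = 6 | L = 11 | L = 17 |
|---|---|---|---|
| 10% | 41.0 | 42.7 | 44.6 |
| 20% | 23.5 | 28.0 | 33.2 |

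At 20% failure the mean number *evaluated* is 17.9, but that is not the number transplanted.

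**5. Earlier information.** The day 112 RNA visit falls 112 − 91 = 21 to 112 − 84 = 28 days after the end of an unextended course, about 8 weeks before the first SVR12 reading (168 − 112 = 56 days).

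**The case against.** The strongest reply is that oversight exists and is continuous. Ad hoc meetings are allowed, events are assessed at each treatment visit, and reports go to the PHRC. HCV RNA is scheduled many times before SVR12, and Section V provides for a response to viremia on treatment. A reader might infer from the missing board that nobody is watching, or that reviewers have no efficacy data until day 168; the documents support neither. What remains is that none of these steps has a defined trigger and none obliges a pause in accrual.

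Three further points stand and limit the remedy:

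- The 5% reference comes from background on many regimens in patients already infected, not from a target set for this trial.
- The denominator is uncertain. Recipients of non-viremic organs may never be treated and should not dilute the rule, so fewer than 50 may count and the chance of detection falls.
- A pause has a price. Waitlisted candidates could not receive these organs meanwhile, and Section VIII notes that some might otherwise die waiting.

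A failure-count boundary also does not monitor rejection, all-cause mortality or drug toxicity, which remain with the existing safety review. Having the same reviewers apply it adds no independence. Their independence cannot be judged either way, because their names are removed from the public text.

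**Conclusion.** The gap is real: by protocol, viremic-graft transplants could continue to the planned maximum however many failures occur, unless someone chooses to pause. A pre-specified boundary is worth adding, but its benefit should be stated modestly. It is strong at 20% failure if about 50 viremic-graft recipients are evaluated (94%), weaker with 25 (73%), and limited at 10% (40% or 24%).

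A reader might take the mean of 18 evaluated patients at 20% failure to mean 18 transplants instead of 50, or conclude that a boundary solves the problem. The readout lag rules out both: the mean is about 24, 28 or 33 transplants with 6, 11 or 17 performed during the lag, and at 10% failure 41 to 45. These figures rest on the assumed 5% reference, accrual of 1 to 3 per month, review after every evaluable patient, and, for the transplant counts, 50 viremic-graft recipients.

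**What to change.** Add to Section IX a pause-and-review rule for new viremic-graft transplants, applied by the existing reviewers and reported to the PHRC. It governs accrual only, not the treatment of any patient. It should state:

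1. **Reference rate.** The acceptable and unacceptable failure rates, with the sponsor confirming or replacing the assumed 5%.
2. **Boundary.** For example, pause at 2 failures within 5 evaluable recipients, 3 within 13, 4 within 22, 5 within 33, 6 within 45, or 7 within 50.
3. **Denominator.** Viremic-graft recipients only; reactively treated recipients of non-viremic organs are tabulated separately.
4. **Failure.** How extended or augmented therapy, a missing SVR12 result, and death or graft loss before SVR12 count.
5. **Earlier signal.** Viremia at the RNA visits already scheduled, such as day 112, is reviewed as it arrives. If it is to count toward the boundary, the operating characteristics must be recomputed.
6. **Operating characteristics.** The probabilities and lag-adjusted transplant counts above, for the expected number of viremic-graft recipients and the expected accrual.

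The cost is a short addition to Section IX, with no extra patients or visits. The downside is a chance of about 5% (25 recipients) to 7% (50 recipients) of an unnecessary temporary pause when true failure is 5%, during which waitlisted candidates could not receive these organs.
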